5 STUDY PLAN AND FLOW CHART

Inclusion and Exclusion Criteria

Inclusion Criteria	Exclusion Criteria	
 Age 18 years or older Resides in the U.S. Speaks, reads, and understands English Has self-reported being diagnosed with any of the following cardiac conditions below in their Achievement profile: Atrial Fibrillation or Afib Abnormal or irregular heart rhythm, other arrhythmic heart disease Cardiac arrest, or heart attack (myocardial infarction) Coronary heart disease like a heart blockage, treated with medications, a stent in the heart, or sometimes bypass surgery Heart failure, like congestive heart failure Stroke or cerebrovascular accident (CVA) 	Participated in Step 1, Part 2 semi- structured interviews used to obtain feedback on the intervention messages.	

Recruitment Methods

Achievement, a product of Evidation Health, is an online platform where people can connect their digital health tools, including wearable activity trackers and fitness apps. Achievement members agree to being contacted with study opportunities when they create an Achievement account. Evidation Health will leverage Achievement for recruitment, and will use an online strategy and study platform to develop a target list of participants, verify eligibility, and enroll participants into this study.

A set of existing Achievement members who have previously self-reported to meeting the inclusion criteria will be tagged for study inclusion, termed "participants" from here on. Since participants will be blinded to their study participation status, participants will not be asked to take any action to enroll in the study. In order to identify a target list of participants, Evidation Health will leverage already permissioned information from Achievement members, including data on their cardiovascular diagnoses, age, sex/gender, race/ethnicity, and country of residence. These participants will be randomized using block randomization into CVD-Intervention or CVD-Control prior to being offered the opportunity to complete any study activities. Randomization will ensure that the groups are representative of the general Achievement population with cardiovascular disease. Efforts will be made to target individuals for enrollment who identify as being of a race/ethnicity that is something other than non-Hispanic White, as well as representative in sex/gender. Participants will be sent offers via the Achievement platform to complete study activities. Participants can complete any number of survey activities (demographics,

[figure not shown]
baseline, 3-month survey, and/or 6-month survey, intervention messages); completion of intervention activities will not be required for enrollment for the CVD-I group.

Study Steps

Participants will be sent an offer to complete a survey at baseline, 3 months, and 6 months, and a demographic and medical history survey will remain available for participants to complete throughout the study. Additional information on study experiences and intervention feedback will be gathered in the 6-month survey for those in the CVD-I group. Data from an activity tracker will be collected if one is already connected to the participant's Achievement account, consistent with their completion of the Data Usage & Permissions Agreement. Activity tracker data will be collected retrospectively and prospectively. Participants in the CVD-I arm only will be sent intervention messages on predetermined days for the duration of the 6-month study intervention period. At the end of the intervention period, individuals who completed a data usage and permissions agreement as a part of the surveys will be informed via email that the survey information they contributed was for a research study investigating influenza vaccination behavior in people with cardiovascular conditions.

Study Compliance

Evidation study staff will track whether participants are completing study-related tasks throughout the study. Participants who do not complete study activities may be contacted by email, text message, or push notifications with reminders to complete activities, within a time window that is appropriate to the specific task, but will remain in the study sample regardless of whether they submit data in a timely manner.

6 MODIFICATIONS TO THE STATISTICAL SECTION OF THE PROTOCOL

The exploratory objective, "To describe self-reported complications from influenza experienced by individuals with different cardiovascular conditions during the 6-month study period, as well as differences in complications by vaccination status" has been removed from analysis because the survey questions did not ask about specific complications of influenza.

7 DATA COLLECTION

- Data from self-reported survey:
 - Demographics
 - Medical history
 - Health behaviors
 - Healthcare utilization
 - o Influenza vaccination status, experience, and complications
 - o COVID-19 experiences
 - Vaccine attitudes and barriers
 - o Influenza risks and healthcare provider role
 - Experience and perceptions of intervention materials (CVD-I only)
- Data from engagement with interventions (CVD-I only)
 - o For example, clicks, dismissals, or completions of interventions
- Data from Achievement Profile
 - Activity data generated by wearables (e.g., heart rate, sleep, step data), from 12 months before participation and 12 months after participation (if available)

	Source	Retrospective 12 months before to 12 months after	Demographics Survey	Baseline	Month 3	Month 6
Self-reported data						
Demographics	Survey		Х			
Medical history	Survey		Х			
Health behavior history & influenza vaccination	Survey		Х			
Healthcare utilization	Survey			Х	Х	Х
Influenza vaccination status	Survey			X	Х	Х
Influenza experience & complications	Survey			Х	Х	Х
COVID-19 experiences & perceptions	Survey			Х	Х	Х
Vaccine drivers & barriers	Survey			Х	Х	Х
Influenza risks & healthcare provider role	Survey			Х	Х	Х
Experience and perceptions of intervention materials	Survey					X (CVD-I only)

Engagement with interventions	Achievement website/app and Survey Monkey		[] (CVD-I only)	
Activity tracker data				
Steps	[e.g. Fitbit, Garmin]	Х	[]	
Sleep	[e.g. Fitbit, Beddit]	Х	[]	
Heart rate	[e.g. Fitbit, Apple]	Х	[]	

7.1 Derived Data

Cardiovascular condition type will be one of the following for the purposes of the secondary analysis objectives:

- People with self-reported arrhythmia only (not including atrial fibrillation)
- People with self-reported atrial fibrillation only
- People with self-reported heart attack, cardiac arrest or coronary artery disease only
- People with self-reported congestive heart failure only
- People with self reported stroke only
- People with two or more of the above conditions
- People with other cardiovascular conditions

Vaccine drivers and barriers of interest include:

- Number of visits to a primary care provider in the 3 months prior (categorized as None, 1-2, 3 or more)
- Number of visits to a cardiology specialist in the 3 months prior (categorized as None, 1-2, 3 or more)
- Hospitalization in the 3 months prior (categorized as none, once, 2 or more)
- Offered influenza vaccination by a healthcare provider (categorized as Yes, No, Unsure)
- Healthcare provider informed individual they were in a 'high risk group' (categorized as Yes, No, Unsure)

Vaccine knowledge factors are based on responses to the survey question "What sources of information do you use to learn about the flu vaccine?", with possible responses:

- Healthcare Professionals
- Family member or peers
- Social media including blog posts
- Mobile applications
- Conventional news media (e.g. television, newspapers)

8 STATISTICAL METHODS

8.1 General Statistical Approaches

For the study variables, we will perform distributional analysis. When describing the study population, we will use min, max, mean, and standard deviations for continuous variables (i.e. age, BMI) and frequency counts for categorical variables (i.e. gender, ethnicity). For both continuous and categorical variables, we will report on the number of participants evaluated for that variable, as well as the number of people with non-missing values. For the study variables, we will also look at individual-level rates of missing data. Missing data or unknown responses will be described separately and not be counted in the summary descriptions of the variables. We will report on the percent of missing data for each of the included data sources (surveys, activity data) and evaluate whether any missingness is associated with baseline participant-level characteristics in the case of missing survey data or with the outcome in the case of activity tracker data.

Statistical testing comparing variables will be performed at the 5% significance level using two-sided tests or two-sided 95% confidence intervals (CI), unless otherwise specified. Comparison of means will use Student's t-test for normal distributions, or a Mann-Whitney U test for non-normal distributions. Comparisons of frequencies will use chi-square tests. Regression modeling approaches are described below. We will report on the size of the beta-parameter estimate and the associated significance level (p-value) for each predictor variable.

8.2 Analysis Population (s)

The analysis populations will consist of:

- P1: This population will consist of all individuals who respond to the 3-month or 6-month survey. It will
 be used for the primary objective analysis and for the first part of the secondary objective (examine
 predictors of vaccination status across the CVD-I and CVD-C arms). This population will also be used
 for the second exploratory objective, which is to describe self-reported complications from influenza
 during the study period.
- P2: This population will consist of all individuals who are in the CVD-I arm and have responded to the 3-month or 6-month survey. It will be used for the second part of the secondary objective, which is to describe the engagement with different intervention messages and its relationship to influenza vaccination status.
- P3a: This population will consist of individuals who responded to the baseline, 3-month or 6-month survey. It will be used to examine the first part of the exploratory objectives - specifically the selfreported impact of COVID-19 on influenza vaccination and behavior.
- P3b: This population will consist of all individuals who complete either the 3-month or the 6-month survey, who have wearable activity data and who consent in the final (6-month) survey to have the activity data analyzed for this study. This population will be used for the 3rd exploratory objective, specifically to explore the differences in wearable data (i.e., sleep, steps, heart rate) between individuals who experience influenza and those who do not, as well as differences in wearable data between cardiovascular conditions.

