#### 2.2. Secondary Objectives

- To examine differences in vaccination rates between individuals in CVD-I who engaged with different numbers of intervention messages, and changes in self-reported vaccination rates following intervention messages
- To describe levels of engagement with the intervention messages and perceptions of the intervention messages within the CVD-I group
- To examine predictors of vaccination status, including cardiovascular condition type, vaccine drivers/barriers, and vaccine knowledge, across diagnoses and within CVD-I and CVD-C groups

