Based on this, we believe that a 3% effect size is a reasonable assumption and that a sample size of approximately 8,000 participants will be needed to detect this difference with a type I error rate of 0.05 and a presumed power of 0.80. A participation drop-off of 67% has been observed for digital interventions for increasing influenza vaccination in people with diabetes (i.e., Samson et al., 2020). A recent internal survey of individuals with cardiovascular disease demonstrated a survey completion rate of approximately 7%, indicating that this population may have lower than expected engagement. Based on these calculations, we plan to recruit approximately 49,000 participants, anticipating that on average, engagement may be approximately 16%. A targeted enrollment list of approximately 49,000 individuals with 16% survey completion would reach the estimated analysis population of 8,000 participants needed.

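### Message engagement is to be described only in CVD-I survey responders, about 16% of the arm, so the reported level is likely to overstate the intervention's reach

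*SAP*

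**What the plan says.** The protocol (2.2, Secondary Objectives) sets the aim: "To describe levels of engagement with the intervention messages and perceptions of the intervention messages within the CVD-I group". Both documents list clicking, opening or completing messages as a secondary endpoint (Protocol 4.2, SAP 3.2).

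SAP 8.2 fixes the population: "P2: This population will consist of all individuals who are in the CVD-I arm and have responded to the 3-month or 6-month survey". It then gives P2 two jobs. The first is description: "It will be used for the second part of the secondary objective, which is to describe the engagement with different intervention messages". The second is to relate engagement to influenza vaccination status.

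The collection table in SAP 7 lists engagement apart from the self-reported data, for CVD-I only, with the source "Achievement website/app and Survey Monkey". The kinds of record are illustrated as "For example, clicks, dismissals, or completions of interventions". On compliance, SAP 5 says "Evidation study staff will track whether participants are completing study-related tasks throughout the study", and people who submit nothing on time stay in the study sample.

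No other section plans a summary of engagement in the whole arm:
- SAP 8.3 reports survey response by arm, not message engagement.
- SAP 8.6.2 is headed as a description of engagement but specifies only a logistic model of vaccination on the number of engaged messages (0 to 6).
- SAP 6, which lists changes from the protocol's statistical section, does not mention a restriction to responders.

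**The concern.** Vaccination status comes from the surveys, so the model relating engagement to vaccination can use only people who answered one. Describing engagement has no such need, because its data come from the website, app and message tool.

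The restriction also selects on something close to the endpoint. Surveys and messages go to the same members through the same platform and are paid in the same points (Protocol 6.5). SAP 4 uses the two ideas interchangeably: it reads a 7% survey completion rate as a sign of low engagement and equates 16% engagement with 16% survey completion. People who answer surveys are therefore likely to be the ones who open messages.

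The share opening or completing messages is the natural measure of how far a pragmatic intervention reached the people it was sent to. In P2, that share describes a self-selected minority of the arm.

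**Working it through.** **Inputs**
- About 49,000 people on the enrolment list, 16% survey completion, analysis population 8,000 (SAP 4: "A targeted enrollment list of approximately 49,000 individuals with 16% survey completion").
- 1:1 allocation (SAP 4).
- Alternative response levels, also from SAP 4: 7% (internal survey in cardiovascular disease) and 33% (1 − 0.67, from the drop-off in the diabetes study).
- Assumption: response is the same in both arms.
- Engagement rates: none in either document, so these are assumptions.

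**The plan's own figure**

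49,000 × 0.16 = 7,840, within 3% of the stated 8,000. In reverse, 8,000 / 0.16 = 50,000, within 3% of 49,000. The planning figures agree apart from rounding.

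**Size of P2**

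CVD-I = 49,000 / 2 = 24,500.

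| Response f | In P2 (24,500 × f) | Left out |
|---|---|---|
| 7% | 1,715 | 22,785 |
| 16% | 3,920 | 20,580 |
| 33% | 8,085 | 16,415 |

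At 16%, 84% of the arm is left out of the description.

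**Overstatement**

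Let eR be engagement in responders, eN engagement in non-responders, and r = eN / eR.

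- Whole-arm engagement = f × eR + (1 − f) × eN
- Overstatement = eR / whole-arm engagement = 1 / [f + (1 − f) × r]

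The ratio depends only on f and r, so no value of eR has to be assumed. For example, at f = 0.16 and r = 0.5 it is 1 / (0.16 + 0.84 × 0.5) = 1 / 0.58 = 1.72.

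| r = eN / eR | f = 7% | f = 16% | f = 33% |
|---|---|---|---|
| 1 (no difference) | 1.00 | 1.00 | 1.00 |
| 0.75 | 1.30 | 1.27 | 1.20 |
| 0.5 | 1.87 | 1.72 | 1.50 |
| 0.25 | 3.31 | 2.70 | 2.01 |
| 0.1 | 6.13 | 4.10 | 2.52 |
| 0 (ceiling, 1/f) | 14.3 | 6.25 | 3.03 |

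**On the percentage scale**

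If 60% of responders engaged (an assumption) and response were 16%, the whole-arm figure would be:
- 60% at r = 1
- 47.4% at r = 0.75
- 34.8% at r = 0.5
- 9.6% at r = 0

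**The case against.** Several points on the other side have weight.

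- *Complete logs are not promised.* Neither document says that usable records exist for every CVD-I participant. This is inferred from the data source and the tracking statement. It is a reasonable inference, but no more than that.
- *The direction is not proved.* Overstatement requires non-responders to engage less than responders. A reader might infer that overstatement is certain. With no engagement rates in the documents, it is only likely, and the no-difference case belongs in the range.
- *A departure from the protocol is not established.* The same protocol objective covers perceptions of the messages, which come only from the 6-month survey. For that half, the CVD-I group cannot mean everyone randomised, and the phrase may serve only to exclude controls.
- *P2 is the right denominator for one purpose.* A reader might infer that P2 engagement would mislead anyone asking whether a small primary effect reflects weak messages or unread ones. The documents do not support that. The primary effect is estimated in P1, the month-3 or month-6 responders of both arms, and P2 is the CVD-I part of P1. For explaining that effect P2 is the matching group, and a whole-arm figure would not be.
- *Permission may limit the logs.* Protocol 6.2 places the notice about behavioural data at the start of each questionnaire, so people who never opened a survey never saw it. A consent waiver is requested, but whether it covers their logs needs confirming. SAP 8.2 does not give this as its reason, and P2 also drops people who answered only the baseline survey and did see the notice.
- *The selection is visible.* P2 is openly defined, and the SAP 8.3 flow chart will show that responders are a minority.

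These points limit the claim to reach in the randomised arm and soften its certainty. None of them explains why P2 should be the only population in which engagement is described.

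**Conclusion.** The point holds as a statement about reach. Following SAP 8.2, a named secondary endpoint would be described in about 3,920 of about 24,500 CVD-I participants, selected by an action that the SAP itself counts as engagement. The result is likely to overstate the intervention's reach in the randomised arm.

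The size cannot be fixed from the documents. It depends on the response rate and on how much less non-responders engage. At the SAP's 16% it runs from no overstatement to a ceiling of 6.25-fold, and the ceiling is 14.3 at 7% response and 3.0 at 33%.

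The matter is confined to a descriptive secondary endpoint. No test, primary estimate or primary conclusion changes, and P2 remains suitable for the vaccination model. It is worth correcting because the correction is cheap.

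**What to change.** In SAP 8.2 and 8.6.2:

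1. Describe opens, clicks and completions, per message and as the 0 to 6 count, in everyone randomised to CVD-I. Count those with no recorded engagement as 0.
2. Show the same summary for P2 beside it, labelled as survey responders.
3. Keep P2 for the model relating engagement to vaccination status and for interpreting the effect estimated in P1.
4. Confirm that the consent waiver covers aggregate use of engagement logs from people who never opened a survey. If it does not, use the widest permitted CVD-I set, which at least adds those who answered only the baseline survey, and report the number sent messages so that readers can see the full denominator.

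The cost is a few lines of SAP text, one more table from records the plan already collects, and the permission check. The whole-arm engagement figure is likely to look less favourable than the P2 figure.

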#### 6.5. Compensation

Participants in both arms will be compensated for completing surveys. Participants in the CVD-I will be compensated minimally for the completion of intervention tasks (e.g., completing short quizzes, scheduling a date for their influenza vaccine, reading an article to learn more about the flu, the flu shot, and their cardiovascular conditions), to avoid incentivizing vaccination status unequally between the two arms. The compensation amounts will be detailed in the Data Usage & Permissions Agreements at the beginning of each survey for CVD-I and CVD-C arms, and in the offer to complete the intervention messages for the CVD-I arm. All compensation will be awarded in Achievement Points, of which 100 points is equivalent to \$0.10. Points can be redeemed for monetary compensation or donated to charitable organizations. The following compensation will be awarded: 50 points per intervention message completed, 3 points per optional informational email requested, and 300 points per survey completed. The maximum number of points possible is 1,518 points, which could be redeemed for approximately \$1.52.

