Cardiovascular condition type is described above in Section 8.1: Derived Data. Vaccine drivers and barriers are described above in Section 8.1: Derived Variables. The beta-parameter estimates, p-values, adjusted odds ratio and 95% CI will be reported. SHapley Additive exPlanations (SHAP) values will be used to assess the individual contributions of each predictor variable [Lundberg, 2017].

To describe the predictors of vaccination status and how it varies between CVD-I and CVD-C, we will use the model:

$$logit(Y) = \beta_0 + \beta_1 P + \beta_2 C + \sum_i \beta_i P_i * C + \sum_i \beta_i \alpha_i + \varepsilon$$

Where the variable *C* is a binary (1,0) designation for CVD-I and CVD-C respectively, and the beta-estimate for interaction term will be reported with the corresponding p-value, adjusted odds ratio and 95% CI. As with above, the SHAP values will be used to evaluate the individual contributions of each predictor variable.

People who report getting the influenza vaccination are asked a series of behavioral and attitudinal questions around where, how and when the vaccination was received. Those survey responses will be summarized for the study population. Similarly, people who did not obtain an influenza vaccine are asked a set of questions around attitudes and willingness to vaccinate, and those will also be summarized. Changes in response to questions on vaccine drivers and barriers will be examined between the baseline survey and the final survey.

8.6.2 To describe engagement with interventions, including clicking, opening, or completing the intervention messages

To examine differences in vaccination rates between individuals in the CVD-I group and its relationship to engagement with intervention messages, we will model:

$$logit(Y) = \beta_0 + \beta_1 M + \sum_i \beta_i \alpha_i + \varepsilon$$

Where:

logit(Y) = In(Y/1-Y) for the binary variable designation of influenza vaccination status M = the number of engaged messages (ordinal variable 0, 1, 2, 3, 4, 5, 6) α_i = the baseline covariates measured in the study (e.g. demographics, CVD type)

- 8.7 Exploratory objective analysis
- 8.7.1 To describe the self-reported impact of the COVID-19 pandemic on influenza vaccination behavior Descriptive summaries of the participant responses to the monthly survey questions on COVID-19 will be

provided.

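### The message-count model in SAP 8.6.2 sets no common follow-up window, so uneven follow-up can produce a dose-response even if the messages have no effect

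*SAP*

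**What the plan says.** SAP 8.2 builds P2 from "all individuals who are in the CVD-I arm and have responded to the 3-month or 6-month survey" and uses it to "describe the engagement with different intervention messages and its relationship to influenza vaccination status". One follow-up survey is enough to enter. SAP 5 allows participants to complete any number of the surveys, so some people will have month 3 only.

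Vaccination status comes from surveys at baseline, month 3 and month 6 (SAP 7). Participants in CVD-I "will be sent intervention messages on predetermined days for the duration of the 6-month study intervention period" (SAP 5, Study Steps).

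The model in SAP 8.6.2 has a single binary status, the exposure "M = the number of engaged messages (ordinal variable 0, 1, 2, 3, 4, 5, 6", and "the baseline covariates measured in the study (e.g. demographics, CVD type" as adjustment. Protocol 8.2.3 has the same structure with a slightly different list of baseline covariates.

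Neither document gives a rule for combining the two surveys into one status, a cut-off date for counting messages, a term for the last survey answered, or an analysis limited to month-6 responders. Estimated vaccination dates are collected, but their only stated analytic use is the Kaplan-Meier curves in SAP 8.5.

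**The concern.** Cumulative vaccination can only rise over a season. A person whose last survey is month 3 has had less time to be recorded as vaccinated than a person who answered at month 6. If the same person also stopped using the platform, fewer messages will have been engaged with. Length of follow-up is then related to both the exposure and the outcome, and a model with baseline covariates alone cannot separate it from a message effect.

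This differs from two other weaknesses of such a model: people who go on engaging after vaccination, and habitual vaccinators who engage more. It can arise even if message count and vaccination are unrelated within each survey group.

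What is at stake is a secondary objective. Protocol 2.2 lists the comparison by number of messages first among the secondary objectives, and a positive per-message odds ratio could be taken as support for the messages.

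**Working it through.** **Inputs from the documents.**
- Analysis population of about 8,000 (SAP 4). The printed formula for 50% versus 53% gives 0.5 × (2.8016 / 0.030018)² = 4,355. Twice that is about 8,710, the tabulated figure, so the tabulated sizes are totals for both arms. At 1:1, P2 is about 8,000 / 2 = 4,000.
- 50% vaccinated by month 6, one of the three baseline rates in SAP 4.
- Two-sided 5% tests (SAP 8.1).
- Six messages. The compensation rules agree: 6 × 50 + 6 × 3 + 4 × 300 = 1,518 if there are six messages, six optional emails and four surveys, and Protocol 6.5 states "The maximum number of points possible is 1,518 points".

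The documents give no figure for the message model itself.

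**Assumptions, not in the documents.** Share *s* of P2 with month 3 only: 20-40%. Late rise in vaccination between months 3 and 6: 0 to 10 points. Engagement per message: 0.25-0.35 in month-3-only people against 0.50 in the rest. M is binomial out of 6. Within each survey group M and vaccination are independent, so the true message effect is nil.

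**Approximation by hand** for *s* = 0.30, a 7.5-point rise (42.5% against 50%) and 0.35 against 0.50:
- Log-odds gap between groups: −ln(0.425 / 0.575) = 0.302.
- Mean M: 6 × 0.50 = 3.0 and 6 × 0.35 = 2.1, difference 0.9.
- Covariance of group with M: 0.3 × 0.7 × 0.9 = 0.189.
- Variance of M: 0.7 × 1.5 + 0.3 × 1.365 + 0.21 × 0.81 = 1.630.
- Spurious slope: 0.302 × 0.189 / 1.630 = 0.035 per message. Odds ratio for 6 versus 0: exp(6 × 0.035) = 1.23.
- Overall rate: 0.7 × 0.50 + 0.3 × 0.425 = 0.4775. Standard error: 1 / √(4,000 × 0.4775 × 0.5225 × 1.630) = 0.0248.
- Rejection: Φ(0.035 / 0.0248 − 1.96), about 29%.

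**Logistic model fitted to the expected cell counts**, n = 4,000:

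| Late rise | Month 3 only | Engagement, month-3-only vs rest | OR, 6 vs 0 | Rejection |
|---|---|---|---|---|
| 0 points | 20-40% | 0.25-0.35 vs 0.50 | 1.00 | 5% |
| 2 points | 20-40% | 0.25-0.35 vs 0.50 | 1.04-1.10 | 6-10% |
| 5 points | 20-40% | 0.25-0.35 vs 0.50 | 1.11-1.26 | 11-38% |
| 7.5 points | 30% | 0.35 vs 0.50 | 1.23 | 29% |
| 10 points | 30% | 0.35 vs 0.50 | 1.32 | 47% |
| 10 points | 30-40% | 0.25 vs 0.50 | 1.50-1.59 | 83-91% |
| 2-10 points | 20-40% | 0.50 vs 0.50 | 1.00 | 5% |

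The first and last rows show that both conditions are needed.

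**A second mechanism.** Suppose engagement per message is 0.50 in everyone, but month-3-only people stop after the first three messages. With a 5-point rise and 20-40% month-3-only, rejection is 21-41%.

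**Check of the remedy.** Adding an indicator for the last survey answered returns the odds ratio to 1.00 and rejection to 5% in every row. In simulations of the second mechanism (600 replicates per scenario, late rises of 2, 5 and 10 points), restriction to month-6 responders gives an odds ratio per message of 0.998-1.001 and rejection of 3.7-5.8%.

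**The case against.** A reader might infer that a positive dose-response is guaranteed by the design. The documents do not support that. It needs a month-3-only group of some size, vaccination after month 3, and lower message counts among month-3-only people. None of these is quantified. With a 2-point late rise the distortion is close to nothing. With engagement of 0.45 against 0.50, 30% month-3-only and a 5-point rise, rejection is about 6%.

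The direction is not certain either. Who answers which survey may depend on vaccination status. If month-3-only responders reported 5 points more vaccination than the others, the 30% and 0.35-versus-0.50 case gives an odds ratio of 0.977 per message.

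The six-month counting window is also an inference, from the 0-6 scale and the message schedule. The SAP states no window, and the available text does not show how the messages are spaced. Early spacing would weaken the link between last survey and count. That uncertainty stands, but an unstated window is itself a gap to close.

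The analysis is non-randomised, within one arm, and sits under a descriptive heading. The SAP makes no causal claim. Response by survey and arm will be reported (SAP 8.3), and missing survey data will be compared with baseline characteristics (SAP 8.1). Readers will therefore see the response pattern, but neither step corrects the model. The covariate list is given as examples, yet it is limited to baseline covariates, and the last survey answered is not one.

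Finally, a common window does not deal with people who keep engaging after vaccination. That stands and limits what the remedy can claim.

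**Conclusion.** The point holds as a conditional one. As written, P2 and SAP 8.6.2 allow length of follow-up to be tied to message count, and nothing in either document removes that link. Under the stated assumptions the effect runs from negligible to large, with an odds ratio of 1.23 and 29% rejection in the 30%, 7.5-point, 0.35-versus-0.50 case. The spread reflects what the documents leave unknown and is not a forecast.

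A reader might also carry this over to the randomised result. The documents do not support that: the mechanism works through the message count, which enters only the within-arm model.

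The change is worth making before analysis because it needs no new data and a named secondary model depends on it.

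**What to change.** In SAP 8.6.2, put messages and vaccination status on one window: fit the model in CVD-I participants who answered the month-6 survey, and state that M counts messages over those six months. As a sensitivity analysis on all of P2, add an indicator for the last survey answered (month 3 only versus month 6) and count only messages sent before the survey that supplies the status. State how the month-3 and month-6 answers combine into one status. Report the result as an association.

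The cost is SAP wording, one model term and some precision. If 20-40% of P2 answered month 3 only, the main model falls from 4,000 to 3,200-2,400 people. From sample size alone the standard error then grows by 1/√0.8 = 1.12 to 1/√0.6 = 1.29. Restriction also selects people who kept participating, which is why the sensitivity analysis keeps everyone. Neither model removes confounding from engagement after vaccination. A time-to-vaccination model using the collected dates, censored at the last survey and with a time-updated message count, would address that more directly, but it is a larger rewrite.
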